2.2 Study Design

MEK-NF-201 is a multi-center, open-label, single-arm, longitudinal, uncontrolled, Phase 2b study to evaluate the efficacy, safety, and tolerability of mirdametinib in participants ≥ 2 years of age with an inoperable NF1-associated PN that is causing significant morbidity.

This study will consist of two phases: the Treatment Phase and the optional Long-Term Follow-Up (LTFU) Phase. Approximately 100 participants will be enrolled and stratified by age (approximately 50 participants 2 to 17 years of age and 50 participants ≥ 18 years of age). The first five participants enrolled in the pediatric cohort must be 9 to 17 years of age at the time of signing informed consent/assent. After the first 5 participants have enrolled in the pediatric cohort, enrollment into this cohort will be paused, and only after Data Monitoring Committee (DMC) evaluation of at least 2 cycles of cumulative safety data for these 5 participants will the pediatric cohort be re-opened and potentially expanded down to 2 years of age. Note the adult cohort will not be affected by this special procedure; participants ≥ 18 years of age will be enrolled continuously from the outset.

Document: S:\Q_146\Q_03974\MEK-NF-201\Prog_Stat\Documentation\SAP\MEK-NF-201 SAP v1.0.0.docx

Participants will be screened for up to 45 days prior to the first dose of study treatment (mirdametinib) and eligibility will be based on the inclusion and exclusion criteria listed in Sections 5.1 and 5.2 of the protocol, respectively. Study treatment will then be administered orally at a dose of 2 mg/m² BID with a maximum dose of 4 mg BID. Dosing in the Treatment Phase will be on a 28-day cycle with a 3 week on/1 week off schedule for up to 24 Cycles. Eligible participants will take their first dose of study treatment following all pre-dose assessments on Cycle 1 Day 1. All participants will remain in the Treatment Phase of the study until radiographic disease progression (confirmed by central review), they discontinue study treatment for any other reason, the study is stopped by the sponsor for any reason, or the participant has completed the study through Cycle 24.

Participants who complete Cycle 24 of the Treatment Phase and did not meet withdrawal criteria detailed in the protocol are eligible to participate in the LTFU Phase. Eligible participants will continue taking the last dose assigned in the Treatment Phase (approximately 2 mg/m² BID [maximum dose of 4 mg BID]) of mirdametinib, on an intermittent (3 weeks on/1 week off) dosing schedule in 28-day cycles. Participants will remain in the LTFU Phase until a withdrawal criterion is met as described in Section 7 of the protocol or mirdametinib is commercially available.

A participant is considered to have completed the Treatment Phase if he/she has completed the Cycle 24 visit (End of Treatment Phase) or has entered the LTFU Phase.

The treatment group labels that will be used in all outputs are presented in Table 2.

Table 2: Study Treatments

Actual Treatment	Treatment Label
PD-0325901 (approximately 2 mg/m ² BID)	Mirdametinib

Table 3 and Table 4 present the visit labels that will be used in all outputs for the Treatment and LTFU Phases, respectively.

Table 3: Study Visits – Treatment Phase

Visit	Visit Label
Screening	Screening
Cycle 1 – Week 1 (Baseline, study visit day 1)	C1D1
Cycle 1 - Week 3 (Cycle Day 15)	C1D15
Cycle 2 – Week 7 (Cycle Day 15)	C2D15
Cycle 3 – Week 11 (Cycle Day 15)	C3D15
Cycle 4 - Week 15 (Cycle Day 15)	C4D15
Cycle 5 – Week 19 (Cycle Day 15)	C5D15
Cycle 6 – Week 23 (Cycle Day 15)	C6D15
Cycle 7 - Week 27 (Cycle Day 15)	C7D15
Cycle 9 – Week 35 (Cycle Day 15)	C9D15
Cycle 11 – Week 43 (Cycle Day 15)	C11D15
Cycle 13 - Week 51 (Cycle Day 15)	C13D15
Cycle 15 – Week 59 (Cycle Day 15)	C15D15
Cycle 17 – Week 67 (Cycle Day 15)	C17D15
Cycle 19 – Week 75 (Cycle Day 15)	C19D15
Cycle 21 – Week 83 (Cycle Day 15)	C21D15
Cycle 23 – Week 91 (Cycle Day 15)	C23D15
Cycle 24 (End of Treatment Phase) - Week 96 (Cycle Day 21)	C24D21
Early Termination	ET
Safety Follow-up – 30 days after last dose	SFU

Document: S:\Q_146\Q_03974\MEK-NF-201\Prog_Stat\Documentation\SAP\MEK-NF-201 SAP v1.0.0.docx

Author:

Table 4: Study Visits - Long-Term Follow-up Phase

Visit	Visit Label
Cycle 28 (Cycle Day 15)	C28D15
Cycle 32 (Cycle Day 15)	C32D15
Cycle 36 (Cycle Day 15)	C36D15
Cycle XX (Cycle Day 15)	CXXD151
End of Treatment	EOT
Safety Follow-up = 30 days after last dose	LTSFU

¹The Long-Term Follow-up phase lasts an indefinite amount of time; visits will occur on day 15 of every 4th cycle with the cycle number inserted into this visit label format.

2.3 Sample Size Determination

Approximately 150 participants will be screened in this study to assure approximately 100 participants are assigned to the open-label treatment with mirdametinib. These 100 participants will be stratified by age, with 50 participants ages 2 to 17 years for the pediatric cohort and 50 participants ≥ 18 years of age for the adult cohort. The sample size was calculated separately for each stratum to allow for different hypothesized magnitudes of response depending on the age group of the participants.

An observed objective response rate (ORR) of at least 42% (at least 21 objective responses) in 50 treated adult participants will result in a lower bound of the 95% confidence interval (CI) that excludes 28%. This will be considered evidence of clinically significant activity of mirdametinib. This is equivalent to testing a null ORR rate of 23% compared to a target rate of 43% with 80% power and 2-sided alpha of 0.05. Similarly, an observed ORR of 64% (at least 32 objective responses) in 50 treated pediatric participants will result in a lower bound of the 95% CI that excludes 49%.

For the analysis of safety, there is a 95% chance of observing at least 1 adverse event (AE) that occurs at an underlying rate of 3.0-% in a sample size of 100 participants.

The assumptions for the response rate in the adult population used for the basis of sample size estimation are based on the study conducted by Weiss et al (Weiss 2017). As outlined in Section 2.1, the preliminary results from this study describe an ORR (as defined by a 20% reduction by of the target lesion from baseline) of 42% (95% Cl: 20% to 67%) in response to one year of mirdametinib therapy. The results of tumor response post-therapy at > 1 year have not yet been released. This finding is consistent with the preliminary data of cabozantinib in patients with a morbid or progressing PN. In a Phase 2 study of cabozantinib in adults > 16 years of age with an evaluable PN, 8 of 19 patients achieved an objective response (42%) (Shih, 2018).

Sample size assumptions for the pediatric population are based on the interim results from the SPRINT study conducted by Gross et al (Gross, 2018). The SPRINT study enrolled 50 patients aged 3-18 years with inoperable morbid PNs. To date, this study has demonstrated a confirmed ORR of 68%. These findings are consistent with the preliminary data of another PN study with trametinib. Twenty-six patients aged 1 to 17 years of age (median 5.5 years) with a measurable PN were treated with trametinib for a median of 61 weeks (range 3 to 124 weeks). In this study, 12 patients (46%) achieved an objective response (Moertel, 2018). Section 5.2 discusses the hypotheses that will be evaluated for the primary efficacy analysis in each age cohort.

Document: S:\Q_146\Q_03974\MEK-NF-201\Prog_Stat\Documentation\SAP\MEK-NF-201 SAP v1.0.0.docx

SpringWorks Therapeutics Protocol Number: MEK-NF-201

2.4 Schedule of Activities

The full schedule of activities (SoA) can be found in Sections 1.3 (Treatment Phase) and 1.4 (LTFU Phase) of the protocol.

Analysis Populations

The analysis populations of interest are:

- Full Analysis Set (FAS)
- Per-Protocol Set (PPS)
- Safety Analysis Set

In addition to these, the Enrolled Set is defined as all participants who signed the ICF and passed Screening.

Each of the analysis populations, as well as their associated criteria for inclusion, are described in the following sections.

3.1 Full Analysis Set

The FAS is defined as participants who received at least one dose of mirdametinib.

The efficacy endpoints will be based on the FAS.

3.2 Per-Protocol Set

The PPS is defined as the set of all participants in the FAS who have completed at least one post-baseline disease evaluation and who do not have any major CSR reportable deviations, including but not limited to efficacy assessments or compliance.

The PPS will be used in a supportive analysis of confirmed objective response rate.

3.3 Safety Analysis Set

The Safety Analysis Set is defined as participants who received at least one dose of mirdametinib. This is an equivalent definition to the FAS.

The Safety Analysis Set will be used for all safety analyses. Since it is equivalent to the FAS, it will not be presented in any baseline summaries such as demographics; instead, the FAS summary will be footnoted to highlight that it is equivalent to the Safety Analysis Set.

4. Study Measures

This section describes the measures that are collected and/or derived during the study at the time points specified in the SoA (Sections 1.3-1.4 of the protocol). This includes efficacy, safety, tolerability, and participant characteristics data.

4.1 Efficacy Measures

The efficacy measures summarized for this study are confirmed ORR, duration of response, quality of life and pain evaluations by PRO, physical function assessments, time to progression, progression free survival, and formulation acceptability by PRO. The endpoints described in this section will be analyzed according to the analysis methods described in Section 6.11.

Document: S:\Q_146\Q_03974\MEK-NF-201\Prog_Stat\Documentation\SAP\MEK-NF-201 SAP v1.0.0.docx

Author:

Baseline efficacy measure values are defined as the most recent assessment taken on or before treatment start date, unless otherwise specified.

4.1.1 Primary Efficacy Measure

The primary efficacy endpoint of interest is the confirmed ORR by the end of Treatment Phase (i.e., Cycle 24). The confirmed ORR is defined as the proportion of participants who have a confirmed ≥ 20% reduction in target tumor volume as compared to baseline as assessed by a BICR, and the response needs to be confirmed by BICR in a consecutive tumor assessment within 2 − 6 months.

To determine the level of target tumor response (complete response [CR], partial response [PR], stable disease [SD], or progressive disease [PD]) which are described below, post-baseline measurement scans are compared to the target PN volume in the pre-treatment MRI scan using volumetric data analysis:

- CR: A complete resolution of the target PN
- PR: A ≥ 20% reduction in the volume of the target PN lesion compared to baseline
- SD: Between a < 20% increase and < 20% decrease in the volume of the target PN lesion compared to baseline
- PD: A ≥ 20% increase in the volume of the target PN compared to baseline. (Radiographic disease progression)

The best overall confirmed response (CR, PR, SD, PD, NE - where SD/PD/NE only require a singular response to be deemed confirmed at that level) will be summarized. For participants that remain on treatment after PD, only the best response up to PD will be considered. For participants who only have one response measurement, and this is a CR or PR (and therefore unconfirmed), their best overall response status will be set to "Missing".

All tumor volume measurements will be independently calculated by two BICR readers. In the case that the two measurements represent different tumor response statuses, as defined above, an independent adjudicator will make the final decision on which response category is recorded at that visit. The primary endpoint analysis will be performed using the adjudicator-selected reader for those visits where the two BICR readers did not agree.

Tumor volume (mL) will be assessed using MRI scans that will be taken at screening, then every 4 cycles at Cycles 5, 9, 13, 17, 21, 24, and ET for the Treatment Phase, and Cycle 28 and every 4 cycles after that, up to and including end of treatment (EOT), for the LTFU Phase, if applicable. Only tumor assessments during the Treatment Phase and prior to the first treatment start date in the long-term follow up will be considered for the determination of confirmed response. Unscheduled visits will be mapped to a visit window based on the criteria in Section 5.6.

The FAS will be used to calculate the confirmed ORR. Participants who do not have a post-baseline MRI assessment or do not achieve a confirmed response will be categorized as non-responders, and their best overall response will be deemed as "Missing".

Document: S:\Q_146\Q_03974\MEK-NF-201\Prog_Stat\Documentation\SAP\MEK-NF-201 SAP v1.0.0.docx

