The approach to treatment of the various tumors associated with NF1 depends upon the type of tumor, its effect on adjacent tissues, and related complications. Plexiform neurofibroma usually involve multiple nerve fascicles, with serpiginous growth and significant vascularity. These lesions can be a significant challenge in surgical treatment and pain management, especially with progressive growth along the spinal column that may result in compression of the spinal cord (Gold 2013). The management of these complex lesions is unclear. In several series, patients were more likely to benefit from surgery when the indications were airway compression or disfigurement (Canavese 2011). However, up to 44% of tumors progress after the first surgery, most commonly in patients younger than ten years of age, with head and neck tumors that could not be completely resected (Needle 1997). Surgical resection often is limited to debulking of a specific area of a large lesion, for example, when a component is impinging on the spinal cord or airway or a large soft tissue component is removed to improve cosmesis. While no specific medical treatment for PNs exists, several therapies have been evaluated.

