- 4. Participant has a target PN that is deemed inoperable, defined as a PN that cannot be completely surgically removed without risk for substantial morbidity due to: encasement of or close proximity to vital structures, invasiveness, or high vascularity of the PN, or the participant refuses surgery. Participants who previously underwent surgery for a PN will be eligible to enter the study after the surgery, provided the PN was incompletely resected and is evaluable by volumetric analysis;
- 5. Participants must have a target PN, defined as the clinically most relevant PN, amenable to volumetric MRI analysis. For the purpose of this study, the target PN must be seen on at least 3 consecutive MRI slices and the field of view must contain the entire tumor of interest. As determined by central radiologic review, a target PN must be analyzable by volumetrics using the REiNS criteria, at least 5 mL in volume, and will be classified as "typical PN", "nodular PN", or "solitary nodular PN" prior to first dose of study treatment;
- 6. Participants ≥ 18 years of age must have a PN amenable to a percutaneous biopsy and must be willing to undergo pre-, and end of treatment tumor biopsies providing fresh tumor tissue; there should be no contraindication for serial biopsy; Participants 2 to 17 years of age should not undergo biopsy unless there is a clinical indication to obtain fresh tumor tissue;
- 7. Participants ≥ 16 years of age must have a Karnofsky performance level of $\geq 50\%$, and participants < 16 years must have a Lansky performance of $\geq 50\%$. Note: Participants who are unable to walk because of paralysis, but who are upright in a wheelchair, will be considered ambulatory for the purpose of assessing the performance score;
- 8. Participant has adequate organ and bone marrow function as defined by the following Screening laboratory values:
 - 8.1. Absolute neutrophil count $\geq 1500 \text{ cells/}\mu\text{L}$;
 - 8.2. Platelets $\geq 100 \text{ x } 10^3/\mu\text{L}$;
 - 8.3. Hemoglobin \geq 9.5 g/dL;
 - 8.4. Serum albumin $\geq 2.8 \text{ g/dL}$;

8.5. Calculated creatinine clearance at Screening ≥ 60 mL/min (by Cockcroft-Gault formula) OR a normal serum creatinine based on age described in the table below;

Age (years)	Maximum Serum Creatinine (mg/dL)
≤5	0.8
$>$ 5 and \leq 10	1.0
> 10 and ≤ 15	1.2
> 15	1.5

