6.5.2. Prohibited or Restricted Concomitant Medications/Treatments

- Prior use of mirdametinib (PD-0325901) or any other MEK 1/2 inhibitor is prohibited.
- Alternative therapy for the treatment of PNs (e.g., farnesyltransferase inhibitors, kinase inhibitors, etc.) within 45 days (or 5.5 half-lives, whichever is longer) of first dose of study treatment and throughout the Treatment Phase or LTFU Phase is prohibited.
- Medical treatment (e.g., chemotherapy, biologic therapy, radiation therapy) directed towards any NF1-related tumor such as optic pathway glioma is prohibited throughout the Treatment Phase or LTFU Phase.
- The use of chronic systemic, inhaled, or ocular glucocorticoid therapy is prohibited within the 14 days prior to first dose of study treatment and throughout the Treatment Phase or LTFU Phase with the following exceptions:
 - Physiologic or stress doses of steroids, when indicated in participants with endocrine deficiencies
 - Glucocorticosteroids given as the premedication for blood product transfusions

- Glucocorticosteroids given as the pulse treatment for an acute allergic reaction or bronchospasm
- Oral or intravenous glucocorticosteroids for up to 6 consecutive days, when indicated for the management of an adverse event only after consultation with the Medical Monitor and/or ophthalmologist
- Topical steroids for dermatological purposes are permitted at the discretion of the Investigator

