4.1.2 Secondary Efficacy Measures

4.1.2.1 Duration of Response

A secondary efficacy objective is to determine the DoR for participants who attain a best confirmed response of PR or CR using BICR MRI volumetric analysis. Confirmed response is defined in Section 4.1.1.

DoR is defined as the time in months between the first instance of response that is subsequently confirmed, until the date of radiographic disease progression or death, whichever occurs first. The DoR will be summarized in months as follows: (date of event (i.e. radiographic disease progression or death) or censoring – date of first response + 1) / 365.25 *12.

For participants who enter the LTFU Phase, all MRI assessments in both the Treatment Phase and LTFU Phase will be used to determine DoR. Those who achieved a DoR of at least 12 months are considered to have experienced a durable response.

Participants without radiographic disease progression or death while on study will have their results censored to their most recent adequate (i.e. evaluable) tumor assessment date.

If participants receive any surgery impacting the target PN or start subsequent systemic therapy for the treatment of PNs prior to radiographic progression, then the participant is censored at the last adequate tumor assessment prior to target PN surgery or subsequent PN treatment. The rules for censoring and events for the duration of response are summarized in Table 5 below.

Table 5: Censoring and Event rules for DoR

Situation	Date of Censoring or Event	Outcome
No adequate tumor assessment post confirmed response	Date of tumor assessment that resulted in response confirmation	Censored
No radiographic disease progression or death post confirmed response	Date of last adequate tumor assessment	Censored
New surgery or subsequent anticancer PN therapy started prior to radiographic disease progression post confirmed response	Date of last adequate tumor assessment before the start of new therapy or surgery	Censored
Two or more consecutive missing or non- adequate tumor assessments post confirmed response	Date of last adequate tumor assessment before the first missing or non-adequate assessment	Censored
Radiographic disease progression that has been verified by BICR post confirmed response	Date of the earliest tumor assessment that results in a finding of progression	Event
Death before radiographic disease progression post confirmed response	Date of death	Event

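### SAP 4.1.1 sets no cut-off at surgery on the target PN, so later scans can count toward the primary ORR even though DoR, TTP and PFS censor there

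*SAP*

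**What the plan says.** **Primary endpoint (SAP 4.1.1).** Response is a reduction of at least 20% from the pre-treatment volume, and "the response needs to be confirmed by BICR in a consecutive tumor assessment within 2" to 6 months. Three rules decide which scans and participants count:

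- Phase: "Only tumor assessments during the Treatment Phase and prior to the first treatment start date in the long-term follow up will be considered".
- Progression: "For participants that remain on treatment after PD, only the best response up to PD will be considered".
- Non-response: "Participants who do not have a post-baseline MRI assessment or do not achieve a confirmed response will be categorized as non-responders".

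None mentions surgery or new PN therapy. SAP 6.11.1 and 6.11.1.1 (PPS analysis, each reader separately) add no such rule.

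**Time-to-event endpoints.** SAP 4.1.2.1 does foresee the event: "If participants receive any surgery impacting the target PN or start subsequent systemic therapy for the treatment of PNs prior to radiographic progression", DoR is censored at the last adequate scan beforehand. SAP 4.1.3.6 and 4.1.3.7 do the same for TTP and PFS.

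**Protocol.** Section 6.5.2 bars alternative therapy for PNs, with an open-ended list whose examples are all drugs. A separate bullet reads "Medical treatment (e.g., chemotherapy, biologic therapy, radiation therapy) directed towards any NF1-related tumor such as optic pathway glioma is prohibited". Neither names surgery, and Section 7.1 does not list surgery as a reason to stop study treatment. Inclusion criterion 4 covers tumors that cannot be completely removed without substantial morbidity, "or the participant refuses surgery". The Introduction notes of PNs: "Surgical resection often is limited to debulking of a specific area of a large lesion".

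**The concern.** The primary objective is the response rate to mirdametinib. Volume removed by a surgeon is not a response to the drug, and the SAP accepts this for three lower-ranked endpoints. For the endpoint that decides the study, a scan after surgery passes both filters (Treatment Phase, no prior PD) and is compared with the pre-treatment volume like any other scan.

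The study is uncontrolled and each cohort is judged on a lower confidence bound, so any misclassification of this kind raises the observed rate and nothing offsets it. If the SAP is silent, whether such scans count would be settled case by case, possibly with the results in view.

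**Working it through.** **1. Reproduce the plan's figures.** Inputs: n = 50 per cohort (SAP 2.3); two-sided 95% Clopper-Pearson interval (SAP 6.11.1); thresholds 23% for adults and 20% for children (SAP 5.2). The lower bound for x responders is the 2.5th percentile of Beta(x, 50 − x + 1).

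- 21/50 gives 28.19%; SAP 2.3 says it excludes 28%. Agrees.
- 32/50 gives 49.19%; SAP 2.3 says it excludes 49%. Agrees.
- Adults need at least 19/50 to exclude 23%. Exact power at a true rate of 43% is 80.4%, against the stated 80%. Agrees.

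**2. Can a surgical reduction meet the definition?** SAP Table 12 puts the Cycle 9, 13, 17, 21 and 24 scans at days 239, 351, 463, 575 and 665.

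- Surgery between Cycles 9 and 13: the next two scans are 463 − 351 = 112 days apart, and 112/365.25 × 12 = 3.7 months, inside the 2 to 6 month window.
- Surgery just before Cycle 21: 665 − 575 = 90 days, or 3.0 months, also inside.

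So surgery at any time up to the Cycle 21 scan leaves two scheduled Treatment Phase scans that could both qualify.

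**3. Effect of one case.** It adds 1/50 = 2 percentage points.

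| Cohort (threshold) | Responders | Lower bound | Excludes threshold? |
|---|---|---|---|
| Adult (23%) | 18/50 | 22.92% | no |
| Adult (23%) | 19/50 | 24.65% | yes |
| Pediatric (20%) | 16/50 | 19.52% | no |
| Pediatric (20%) | 17/50 | 21.21% | yes |

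**4. Distance from the boundary at rates the SAP quotes.**

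- Adults at 21/50: 21 − 18 = 3 surgical responders would have to be removed before the cohort failed.
- Children at 32/50: 32 − 16 = 16.
- Children at the 44% central-review rate in SAP 7.1 (22/50): 22 − 16 = 6.

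**5. Effect on false-positive risk.** Let k participants be surgical responders and let the other 50 − k respond at the threshold rate p0. Then the probability of success is P(Binomial(50 − k, p0) ≥ r − k), with r = 19 for adults and 17 for children. The values of k are assumptions.

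| k | Adult | Pediatric |
|---|---|---|
| 0 | 1.2% | 1.4% |
| 1 | 2.1% | 2.6% |
| 2 | 3.5% | 4.4% |
| 3 | 5.6% | 7.2% |

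The upper-tail 2.5% is passed at k = 2 in adults and k = 1 in children.

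**6. Knock-on in DoR.** SAP 4.1.2.1 computes (censoring date − first response date + 1)/365.25 × 12. For surgery after Cycle 9 and first response at Cycle 13, the prose censors at day 239: (239 − 351 + 1)/365.25 × 12 = −3.6 months. The Table 5 surgery row is limited to the period after confirmed response, so it does not reach this participant. Prose and table disagree.

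**The case against.** The strongest reply is that the event is unlikely and partly handled elsewhere.

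- *Rarity.* The tumor must be inoperable, and those who enter because they declined surgery have only just declined it. Surgery must also leave at least a 20% net reduction on two scans. This stands: the event is probably rare, and no rate is given.
- *Prohibition.* A reader might infer that the protocol permits target-PN surgery. The documents do not settle this. The alternative-therapy bullet in Section 6.5.2 is open-ended and could be read to include surgery. Systemic PN therapy is plainly prohibited there, and needing a prohibited medication is a listed reason to stop.
- *Discontinuation.* If surgery ended treatment, at most an early termination scan would follow, required only if no MRI was done in the previous 3 months. The main route would then close, although that scan could still confirm a reduction first seen before surgery.
- *PPS.* A reader might infer that no planned analysis could remove such a participant. That goes too far. SAP 3.2 and 4.3.2 exclude deviations that may affect the reliability of efficacy data, and surgery could be judged one. The FAS primary result would not change.
- *Central review.* Readers might call a post-surgical scan not evaluable. The imaging manuals are not in the documents, and nothing supplied ties that category to surgery.

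These replies lower the likelihood. None supplies the missing rule.

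**Conclusion.** The gap is real and should be fixed. As written, a participant who is debulked, stays in the Treatment Phase and has two consecutive qualifying scans is a confirmed PR in the primary analysis unless central review declares the scans not evaluable. The same gap applies to scans after subsequent systemic PN therapy. The bias runs only in the drug's favor, at 2 percentage points per case in a cohort of 50.

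A reader might infer that one such case would overturn the study. The calculation does not support that: one case reverses a conclusion only at exactly 19/50 adults or 17/50 children, and at the rates the SAP quotes it would take 3, 6 or 16. Nor can it be said that ORR will in fact be biased, since the frequency of on-study surgery is unknown. A reader might also infer that DoR must come out negative for such a participant; that follows from the DoR prose but not from Table 5, so the finding there is a conflict between the two.

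**What to change.** Add to SAP 4.1.1: *Only adequate scans before any surgery affecting the target PN, or before the start of subsequent systemic PN therapy, are used for best overall confirmed response. A participant without both a response and its confirmation by that date is a non-responder.*

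Apply the same cut-off to the tumor-volume and best percentage change summaries (SAP 4.1.3.10 and 6.11.3.6). Time to response follows automatically because it is defined on confirmed responders. DCR will rarely move because stable disease already counts. With this rule, no one can enter the DoR set on a response first seen after surgery, which removes the conflict between the prose and Table 5. This changes the analysis only and takes no position on whether surgery should be allowed.

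The cost is SAP wording. Procedures are already collected on the Concomitant Procedures CRF page (SAP 4.3.6), but someone must check that the page shows whether the target PN was involved. Sample size, thresholds and nominal power do not change. ORR can only stay the same or fall slightly, and if no such surgery or therapy occurs it is unchanged.
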